ADJUVANT MUCOSAL THERAPY IN HIV-INFECTED MEN WITH INSUFFICIENT RESPONSE TO ANTIRETROVIRAL THERAPY

Protocol Identification Number: OUSHIVProbiot2

SPONSOR:

Oslo University Hospital

Contact:

Head of Department [name]

Department of Infectious Diseases

Address: [name]
OSLO, Norway

[contact]

E-mail: [contact]

PRINCIPAL INVESTIGATOR (PI):

[name] PhD

Department of Infectious Diseases

Oslo University Hospital

Address: [name]
OSLO, Norway

[contact]

E-mail: [contact]

PROTOCOL VERSION NO. 3.1 - 18.12.2015

CONTACT DETAILS

Sponsor:	Oslo University Hospital [name] [contact] E-mail: [contact] Contact: Head of Department [name], Department of Infectious Diseases
Principal Investigator :	Clinical investigator [name] PhD Department of Infectious Diseases Oslo University Hospital [name] [contact] E-mail: [contact]
Participating Departments:	[name] PhD Head of R&D, Department of Infectious Diseases Oslo University Hospital [name] [contact] E-mail: [contact]
	Head of Department [name] PhD Department of Gastroenterology Oslo University Hospital [name] [contact] E-mail: [contact]
	[name], MD PhD Department of Pathology Oslo University Hospital [name] [contact] E-mail: [contact]
Monitor:	Avdeling for klinisk forskningsstøtte Oslo University Hospital [name] [contact] E-mail: [contact]

SIGNATURE PAGE

Title Adjuvant mucosal therapy in HIV-infected men with insufficient response to antiretroviral therapy

Protocol ID no: OUSHIVProbiot2

I hereby declare that I will conduct the study in compliance with the Protocol, ICH GCP and the applicable regulatory requirements:

Name	Title	Role	Signature	Date
[name]		Sponsor Contact		
[name]		Principal Investigator		
[name]		Participating Scientist		
[name]		Participating Scientist		
[name]		Participating Scientist		

PROTOCOL SYNOPSIS

Title:

Adjuvant mucosal therapy in HIV-infected men with insufficient response to antiretroviral therapy

Sponsor	Oslo University Hospital
Phase and study type	Phase I single arm, open label, consecutive case series study, and subsidiary cross-sectional case control study.
Investigational product (including active comparator and placebo) :	IDOFORM®Travel No placebo/active comparator
Centers:	Oslo University Hospital (single center)
Study Period:	Estimated date of first patient enrolled: 01.12.2015 Anticipated recruitment period: 18 months Estimated date of last patient completed: 30.11.2017
Treatment Duration:	8 weeks
Follow-up:	One follow-up consultation 2 weeks after completed therapy
Objectives	Primary: Assess the safety of a probiotic compound (IDOFORM®Travel) in combined anti-retroviral therapy (cART)-treated immunologic non-responder (INR) patients with chronic HIV infection. Secondary: i) Explore the biological effects of probiotics in cART-treated INR patient with chronic HIV infection; and ii) investigate differences between cART-treated HIV-infected INR and non-INR patients with regards to gut microbiome and mucosal barrier function.
Endpoints:	Primary endpoints: i) Adverse effects; ii) Δ plasma viral load; and iii) Δ blood CD4 count. Secondary/Exploratory endpoints: Alterations in i) Gut microbiota composition; ii) Gene expression of gut epithelial cells; iii) Frequency and activation status of CD4+ T cell subsets in gut lamina propria, including Th17 and Th22 subsets; iv) Frequency, activation status and intracellular signaling of systemic T cells; and v) Soluble

	systemic markers of chronic inflammation and immune activation.
Study Design:	
 1) Single arm, open label, consecutive case series, single center intervention study on cART-treated INR patients with chronic HIV infection 2) Subsidiary cross-sectional case control, single center study comparing cART-treated INR patients with chronic HIV infection to non-INR patients with chronic HIV infection and to healthy controls.
Main Inclusion Criteria:	
 1) Subjects may be included as cases in the study if they meet all of the following criteria: 
 • HIV seropositive >4 years. • Continuous cART >4 years. • Plasma HIV RNA <50 copies/mL >3,5 years.¹⁾ • CD4+ T cell count <400 cells/μL >3.5 years.²⁾ • Male, Caucasian • Age 25-65 • Signed informed consent and expected cooperation of the patients for the treatment and follow up must be obtained and documented according to International Committee on Harmonization (ICH) Good Clinical Practice (GCP), and national/local regulations. 2) Subjects may be included as control subjects in the sub-study if they meet all of the following criteria: 
 • HIV seropositive >4 years. • Continuous cART >4 years. • Plasma HIV RNA <50 copies/mL >3,5 years.¹⁾ • CD4+ T cell count >600 cells/μL >3.5 years. • Male, Caucasian • Age 25-65 • Signed informed consent and expected cooperation of the patients for the treatment and follow up must be obtained and documented according to ICH GCP, and national/local regulations. 
OR if they meet all the following criteria:
 
 • HIV seronegative. • Male, Caucasian • Age 25-65 • Signed informed consent and expected cooperation of the patients for the treatment and follow up must be obtained and documented according to ICH GCP, and national/local regulations.

	
¹)One single measurement (“blip”) of HIV RNA >50 copies/ml accepted.
 
²)One single measurement (“blip”) of CD4 >400 cells/μl accepted.

Main Exclusion Criteria	
Subjects must be excluded from participating in this study if they meet any of the following criteria:
 
 • Plasma hepatitis C (HCV) RNA positive. • Serum hepatitis B surface antigen (HBsAg) positive. • Comorbidity of inflammatory bowel disease, coeliac disease or malnutrition. • Concomitant use of non-steroid anti-inflammatory drugs (NSAID), corticosteroids, disease-modifying antirheumatic drugs, or other anti-inflammatory pharmaceutical substances. • Concomitant use of antithrombotic pharmaceutical substances • Regular (weekly) use of any probiotic substance within 3 months prior to inclusion. • Use of antibiotics within 3 months prior to inclusion. • Deranged liver function (serum albumin <25 g/L or Child-Pugh ≥10) • Renal failure (estimated glomerular filtration rate (eGFR) <30 ml/min) • Heart failure (NYHA class II-IV) • Any reason why, in the opinion of the investigator, the patient should not participate.
Sample Size:	
20 INR patients for intervention study and subsidiary cross sectional study. 20 non-INR case controls and 20 HIV negative healthy volunteers for subsidiary cross sectional study.

Efficacy Assessments:	
The primary objective of this study is safety assessments (see below). Efficacy assessments are exploratory secondary objectives and consist of:
 
 – Mucosa-adherent microbial composition – Gene expression of mucosal tissue with validation of protein expression – Frequency and activation status of LPMC subsets by flowcytometry

	
 – Alterations in systemic T cells intracellular signaling – Soluble markers of chronic inflammation and immune activation.
Safety Assessments:	
 – Self-reported adverse events – Physical examination – Vital signs – Medical biochemistry – HIV RNA quantification – CD4 T cell count

TABLE OF CONTENTS

CONTACT DETAILS.....	2
SIGNATURE PAGE.....	3
PROTOCOL SYNOPSIS	4
TABLE OF CONTENTS	8
LIST OF ABBREVIATIONS AND DEFINITIONS OF TERMS	11
1 INTRODUCTION	13
1.1 Background – Disease	13
1.2 Background - Therapeutic Information.....	14
1.3 Rationale for the Study, Hypotheses and Purpose	14
2 STUDY OBJECTIVES AND RELATED ENDPOINTS.....	15
2.1 Primary Endpoint	15
2.2 Secondary Endpoints.....	15
3 OVERALL STUDY DESIGN	16
4 STUDY POPULATION	17
4.1 Selection of Study Population	17
4.2 Number of Patients	17
4.3 Inclusion Criteria	17

cART	combined antiretroviral therapy
CD n	cluster of differentiation n
Cfu	colony forming units
CK	creatin kinase
CRF	case record form
CRP	C-reactive protein
CTCAE	Common Terminology Criteria for Adverse Event
GCP	Good Clinical Practice
HBsAg	hepatitis B surface antigen
HBSS	Hank's Balanced Salt Solution
HCV	hepatitis C
HIV	human immunodeficiency virus
ICH	International Conference on Harmonization
INR	immunological non-responder
LPMC	lamina propria mononuclear cells
NSAID	non-steroid anti-inflammatory drug
OUH	Oslo University Hospital
PBMC	peripheral blood mononuclear cell
PBS	phosphate buffered saline
PI	principle investigator
qRT-PCR	quantitative reverse transcriptase polymerase chain reaction
R&D	research and development

REK	Regional komite for medisinsk og helsefaglig forskningsetikk, Ethics Committee
RNA	ribonucleic acid
SAE	serious adverse event
SLV	Statens legemiddelverk, Norwegian Medicines Agency
SOP	standard operating procedure
SUSAR	suspected unexpected serious adverse reaction
Th _n	T helper cell type n
Tregs	regulatory T cells
UiO	University of Oslo
CPT	cell preparation tube
CTCAE	Common Terminology Criteria for Adverse Events
H ₀	null hypothesis

1 INTRODUCTION

1.1 Background – Disease

Human immunodeficiency virus-1 (HIV) is a retrovirus that is transmitted between humans by sexual contact and inoculation of blood, including perinatal mother-to-child transmission. The virus infects and kills subsets of T-lymphocytes characterized by cell surface expression of cluster of differentiation (CD)4+. As CD4+ T cells are essential for cellular immunity, natural HIV infection will in most humans destruct the immune system and progress to acquired immunodeficiency syndrome (AIDS), which leads to advanced immunodeficiency, opportunistic infections and eventually death.(1) HIV infection provides a substantial disease burden to global health. More than 36 million people live with HIV infection globally and the virus annually causes 1.5 million deaths.(1, 2)

There is still no cure to eradicate the HIV virus from an infected patient. However, since late 1990s combined antiretroviral therapy (cART) has been available. A combination of at least three pharmaceutical substances prevents the virus from replicating and may subsequently allow the immune system to reconstitute.(3, 4) Patients responding to therapy will have undetectable virus in the blood, and CD4+ T cell numbers should eventually be restored to normal levels (>500 cells/ μ L).(4) Successful cART stops progression to AIDS and confers life expectancy comparable to the general population.(5-7)

Around 15% of cART treated patients do not achieve the treatment goal of CD4+ T cell count of >500 cells/ μ L despite persistent virological suppression.(8, 9) These immunological non-responders (INR) patients (aka discordant responders) have increased risk of still developing AIDS,(10, 11) increased risk of non-AIDS HIV-related morbidity such as cardiovascular disease and cancer, and increased mortality.(12-16) As both absolute and relative numbers of HIV-patients on cART increases globally,(2) efforts to improve the clinical prognosis in patients not responding to cART should be emphasized.

Patients with chronic HIV infection have a chronic low-grade inflammation and immune activation with hyperactivated T cells and subsequent T cell exhaustion.(17) This immune activation is considered to contribute to non-AIDS morbidity and correlates with mortality among HIV patients.(18-20) Immune activation correlates inversely with CD4 T cell counts and INR patients have augmented immune activation.(21-26)

Primary infection with the HIV virus causes massive depletion of CD4 T cells in the gut mucosa, which is only partially restored after years of cART.(27-30) These depleted CD4+ T cells, primarily of the subsets T helper cells type (Th) 17 and Th22, are crucial for maintaining the epithelial barrier and mucosal homeostasis.(31-36) Patients with chronic HIV infection has an impaired gut epithelial barrier with markers on increased epithelial apoptosis and disrupted tight junctions.(37, 38) The impaired epithelial barrier is thought to allow influx of microbial products into systemic circulation, a phenomenon called microbial translocation.(39, 40) Increased microbial translocation is a prime candidate mechanism to explain why INR cART-treated patients do not respond sufficiently to cART, have increased immune activation, and unfavorable clinical prognosis.(23, 24, 40-42) However, *in situ* mucosal assessment in order to prove that the mucosal barrier is impaired in INR patients compared to cART responders is yet to be performed. In depth focal assessments of mucosal barrier function may also disclose perturbations in the regulation of the mucosal barrier that could provide targets for adjuvant therapy to cART.(37, 43) Restoration of mucosal barrier may reduce immune activation and subsequently improve the clinical prognosis for INR HIV-infected patients.

Over the last years there has been an emerging interest in the role of the gut microbiota for health and for chronic diseases, including HIV infection.(44) Alterations in gut microbial composition have been demonstrated in chronic HIV infection.(45-48) Recently published data indicates that the composition of the microbiota correlates directly with the function of the mucosal CD4+ T cells in HIV patients (49) and also

with systemic markers of microbial translocation and immune activation.(50-54) However, the full implications for these observations with regards to epithelial barrier function are still uncertain. As these studies are all cross-sectional observations, it is not known if it is the microbial alterations that causes the altered T cell dysfunction and immune activation or vice versa. Moreover, the relevance of these observations in INR cART treated HIV-infected patients has not been assessed. On the basis of published data referred to above we hypothesize that the perturbations in the axis of gut microbiota -> epithelial barrier impairment ->Th17/Th22 disruptions ->chronic immune activation is greater in INR patients than those responding to cART.

1.2 Background - Therapeutic Information

Probiotics are bacteria that may colonize the gut lumen and provide beneficial health effects, though the mechanisms of how they confer these effects are still largely unknown. (55, 56) We have already conducted a study of administering probiotics in treatment-naïve HIV patients and demonstrated reduction in immune activation in these patients.(57) Other small, preliminary studies have shown similar results.(58, 59) As argued in section 1.1, the increasing fraction of HIV patients on cART makes the relevance of adjuvant probiotic supplement higher in INR cART-treated patients than in treatment-naïve patients, but intervention studies with probiotics in INR HIV patients have not been performed.

Probiotics are generally well tolerated and smaller studies with other probiotic formulas of lower dose have been well tolerated in HIV-infected patients.(58-60) Still, cases of septicemia in young children and adults with compromised immunity have been observed.(61, 62) As our study population has impaired immunity we find it warranted to perform a phase I safety assessment of probiotic compounds before initiating larger efficacy studies in cART-treated INR HIV-infected patients.

1.3 Rationale for the Study, Hypotheses and Purpose

Based on the scientific knowledge presented above we find it warranted to test the following hypotheses:

- i) CART-treated chronic HIV-infected INR patients have an altered composition of their gut microbiota compared with HIV-infected cART-treated immunological responder patients.
- ii) CART-treated chronic HIV-infected INR patients have impaired gut mucosal barrier function compared with HIV-infected cART-treated immunological responder patients, and this dysfunction relates to perturbations in mucosal Th17 and Th22 CD4+ T cells.
- iii) Administration of probiotics to INR cART-treated chronic HIV-infected patients is safe and coincide with alteration of gut microbiota and restoration of mucosal barrier function and reduced systemic immune activation.

To this date there are no scientific publications answering these hypotheses. Exploration of these queries may provide targets for adjuvant therapy in substantial number of patients not responding sufficiently to cART and thereby improve their clinical prognosis.

2 STUDY OBJECTIVES AND RELATED ENDPOINTS

The **primary objective** of this study is to assess the safety of probiotics in cART-treated INR patient with chronic HIV infection.

The **secondary objectives** are to i) explore the biological effects of probiotics in cART-treated INR patient with chronic HIV infection, and ii) investigate differences between cART-treated HIV-infected INR and non-INR patients with regards to gut microbial composition and mucosal barrier function.

2.1 Primary Endpoint

i) Adverse effects; ii) Δ plasma viral load; and iii) Δ blood CD4 count.

2.2 Secondary Endpoints

Alterations in i) Gut microbiota composition; ii) Gene expression of gut epithelial cells; iii) Frequency and activation status of CD4+ T cell subsets in gut lamina propria, including Th17 and Th22 subsets; iv) Frequency, activation status and intracellular signaling of systemic T cells; and v) Soluble systemic markers of chronic inflammation and immune activation.

	Objectives	Endpoints	Assessments
Primary	Assess the safety of probiotics in cART-treated INR patient with chronic HIV infection.	
– Adverse effects– ΔPlasma HIV viral load– ΔBlood CD4 count.	Sections 7.2
Secondary/ Exploratory	Explore the biological effects of probiotics in cART-treated INR patient with chronic HIV infection.	
– Alteration in gut microbiota composition.– Alteration in gene expression of gut epithelial cells– Alteration in frequency and activation status of CD4+ T cell subsets in gut lamina propria, including Th17 and Th22 subsets.– Alteration in frequency, activation status and intracellular signaling of systemic T cells.– Alteration in soluble systemic markers of chronic inflammation	Section 7.1

		and immune activation.	
	Investigate differences between cART-treated HIV-infected INR and non-INR patients with regards to gut microbial composition and mucosal barrier function.	
 – Alteration in gut microbiota composition. – Alteration in gene expression of gut epithelial cells – Alteration in frequency and activation status of CD4+ T cell subsets in gut lamina propria. – Alteration in frequency, activation status and intracellular signaling of systemic CD4+ T cells. – Alteration in systemic markers of chronic inflammation and immune activation. 	Section 7.1

3 OVERALL STUDY DESIGN

[figure not shown]
The primary study is a phase I, single arm, open label, consecutive case series study examining the safety of IDOFORM®Travel in patients with a confirmed diagnosis of HIV infection and continuous cART treatment >4 years and concurrent HIV (ribonucleic acid) RNA <50 copies/mL and CD4+ count <400 cells/μL >3.5 years prior to inclusion. There will be no control arm to the intervention. The primary objective is safety assessment. The secondary objective is exploratory. End points at the termination of the intervention will be compared to the parameters at inclusion. (See chart below.)

Study Period	Estimated date of first patient enrolled:	01.12.2015
	Anticipated recruitment period:	18 months
	Estimated date of last patient completed:	30.11.2017
Treatment Duration:	8 weeks	
Follow-up:	Follow-up terminated at termination of treatment	

In a subsidiary cross sectional case control study, the patients included in the intervention will at baseline (week 0) be compared with individuals with chronic HIV infection and continuous cART >4 years and concurrent HIV RNA <50 copies/mL and CD4+ count >600 cells/μL >3.5 years prior to inclusion, and with

HIV uninfected individuals, both control groups matched to cases with regards to gender, ethnicity, age, and comorbidity

Project scheme

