4.3 Inclusion Criteria

- 1) Subjects may be included as **cases** in the study if they meet all of the following criteria:

- HIV seropositive >4 years.
- Continuous cART >4 years.
- Plasma HIV RNA <50 copies/mL >3,5 years.¹⁾
- CD4+ T cell count <**400 cells/μL** >3.5 years.²⁾
- Male, Caucasian
- Age 25-65
- Signed informed consent and expected cooperation of the patients for the treatment and follow up must be obtained and documented according to International Committee on Harmonization (ICH) Good Clinical Practice (GCP), and national/local regulations.

2) Subjects may be included as **control** subjects in the sub-study if they meet all of the following criteria:

- HIV seropositive >4 years.
- Continuous cART >4 years.
- Plasma HIV RNA <50 copies/mL >3,5 years.¹⁾
- CD4+ T cell count >**600 cells/μL** >3.5 years.
- Male, Caucasian
- Age 25-65
- Signed informed consent and expected cooperation of the patients for the treatment and follow up must be obtained and documented according to ICH GCP, and national/local regulations.

Or if they meet all the following criteria:

- HIV seronegative.
- Male, Caucasian
- Age 25-65

Signed informed consent and expected cooperation of the patients for the treatment and follow up must be obtained and documented according to ICH GCP, and national/local regulations.

¹⁾One single measurement ("blip") of HIV RNA >50 copies/ml accepted.

²⁾One single measurement ("blip") of CD4 >400 cells/μl accepted.

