6.2 By Visit

Informed consent:

Informed consent must have been given by each subject before any study specific procedures are initiated, preferably at screening visit. The following tests will be done at screening:

Clinical status and Vital signs:

Medical history (including disease history and corresponding treatment details), physical examination (eg. cor/pulm/abdomen and peripheral lymph node status), and vital signs (weight, blood pressure, temperature and pulse).

Before vital signs are measured, the subject should be resting seated for at least 2 minutes. Any vital sign value after start of treatment that is judged by the investigator as a clinically significant worsening compared to previous exam will be considered an adverse event (AE), documented on the subject's CRF, and followed until the outcome is determined.

Concomitant medication:

All concomitant medication (incl. herbal preparation and other “over-the-counter” drugs) used by the subject within 28 days of treatment start must be recorded in the CRF. Check boxes in CRF for NSAID, glucocorticoids, disease-modifying antirheumatic drugs, and other anti-inflammatory drugs, antithrombotic drugs, antibiotics (within 3 months) and probiotics (within 3 months)

Clinical chemistry and Biological markers:

Blood samples will be taken to determine clinical chemistry analyses and biological markers.

Clinical chemistry include (one 4 ml sample tube of EDTA whole blood and one 5 ml sample Serum Separation Tube): hemoglobin, white blood cells differential count, thrombocytes, mean corpuscular hemoglobin, mean corpuscular volume, HbA1c, vitamin B12, folate, bilirubin, uric acid, C-reactive protein (CRP), sodium, potassium, creatinine, aspartate aminotransferase, alanine aminotransferase (ALAT), gamma-glutamyl transferase, lactate dehydrogenase, alkaline phosphatase, albumin, amylase, creatin kinase (CK), and lipid profile.

Biological markers include (one 2,5 ml sample tube of EDTA whole blood and one 5 ml sample Plasma Preparation Tube): CD4+ and CD8+ T cell counts and HIV RNA quantification.

In addition the following material will be collected from included subjects for exploratory assays and analyses: One 4 ml sample tube of EDTA whole blood, one 3.5 ml sample Citrate-Na tube, one 5 ml sample of Plasma Preparation Tube (CPT), and one 5 ml sample Serum Separation Tube and eight 7 ml samples Cell Preparation Tubes.

Adverse events:

See section 8.

Colonoscopy:

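### The exploratory INR versus non-INR comparison neither matches on nor adjusts for years on cART, so any difference in treatment length between the two HIV-infected groups could create or hide an apparent INR effect

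*Combined protocol and SAP*

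**What the plan says.** The secondary objective in question (section 2) is to "investigate differences between cART-treated HIV-infected INR and non-INR patients with regards to gut microbial composition and mucosal barrier function". Its endpoints in section 2.2 include "Frequency and activation status of CD4+ T cell subsets in gut lamina propria, including Th17 and Th22 subsets".

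On comparability of the groups:

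- Section 3 has "both control groups matched to cases with regards to gender, ethnicity, age, and comorbidity".
- Section 4.3 requires "Continuous cART >4 years" of INR cases and HIV-infected controls alike, together with more than 3.5 years of HIV RNA below 50 copies/mL. Neither group has a maximum.
- The groups are separated by CD4 count. Cases must have been below 400 cells/μL for more than 3.5 years. Section 3 has them "compared with individuals with chronic HIV infection and continuous cART >4 years and concurrent HIV RNA <50 copies/mL and CD4+ count >600 cells/μL >3.5 years".
- Section 4.1 recruits both HIV-infected groups from the same outpatient clinic.

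On analysis, section 10.4 tests single variables across the three groups by one-way ANOVA with Bonferroni post-tests, and microbiota composition, tentatively, by principal components and a Monte Carlo permutation test. No covariate appears in either. Section 10.3.1 summarises medical history by counts and does not mention years on cART. Section 10.4 also states that no separate SAP exists.

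**The concern.** All participants are male and Caucasian by eligibility, so the matching does real work only on age and comorbidity. Length of background treatment is left free above the floor.

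The protocol's own background makes that length relevant on both sides of the comparison. On the outcome side, section 1.1 describes "massive depletion of CD4 T cells in the gut mucosa, which is only partially restored after years of cART" and says that these cells maintain the epithelial barrier. On the group side, it says of patients who respond to therapy that "CD4+ T cell numbers should eventually be restored to normal levels", and CD4 count is what assigns a man to one group or the other. A variable that may be tied to both group and outcome, and is neither balanced nor modelled, is a candidate confounder.

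Hypotheses i and ii in section 1.3 rest on this contrast. If treatment length differs between the groups, a difference in microbiota, barrier function or lamina propria T cells cannot be assigned to INR status, and the absence of a difference cannot be read as reassurance.

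**Working it through.** **The plan's own figure.** There is none for this comparison; section 10.1 calls sample size calculation for the secondary objectives infeasible. The only figures are the Clopper-Pearson intervals for safety. They reproduce: 0/20 gives an upper limit of 1 − 0.025^(1/20) = 16.8% (stated as 17%), and 1/20 gives 0.13% to 24.9% (stated as 0.1% to 25%). They do not bear on this point.

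**Inputs from the documents.** 20 men per group and three groups (section 4.2); two-sided 5% level and Bonferroni post-tests (section 10.4). Three pairwise comparisons give 0.05/3 = 1.67% each. With 60 men the pooled error has 60 − 3 = 57 degrees of freedom, and the critical |t| is 2.47.

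**Assumptions.** The documents give no spread of cART duration and no rate of mucosal recovery. I take a gap Δ of 0.5 or 1 SD of duration between the HIV-infected groups, a within-group correlation r of 0.3 or 0.5 between duration and marker, unit marker SD, and no INR effect.

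**Formula.** The spurious shift is d = rΔ. The post-test statistic is then noncentral t with λ = d√(n/2) = d × √10 = 3.16d. For Δ = 1 and r = 0.5: d = 0.5, λ = 1.58, and P(|t| > 2.47) = 19.7%.

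The last column shows masking. It takes a true INR difference of 1.06 SD, which the post-test detects with 81% power when durations are equal, and lets the duration shift oppose it, leaving 1.06 − d.

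| Δ (SD) | r | d | False INR finding, nominal 1.7% | Power for 1.06 SD when opposed |
|---|---|---|---|---|
| 0.5 | 0.3 | 0.15 | 2.9% | 66% |
| 0.5 | 0.5 | 0.25 | 5.3% | 54% |
| 1.0 | 0.3 | 0.30 | 7.1% | 48% |
| 1.0 | 0.5 | 0.50 | 19.7% | 25% |

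A simulation of the three-group post-test (20,000 trials per row) gave 2.9%, 5.4%, 7.0% and 19.6% for the false-finding column.

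**On the scale of years.** Assume a within-group SD of 4 years, all durations above the 4-year floor, and a marker slope of 0.05 to 0.15 residual SD per year. A two-group t-test at 0.05/3 then gives about 1.5% with no gap, 2% to 6% with a 2-year gap, 4% to 22% with a 4-year gap and 6.5% to 50% with a 6-year gap.

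**With adjustment.** In the four table scenarios, rank regression on group and duration rejects in 4.9% to 5.4% of trials at 0.05, and in 1.7% to 1.9% at 0.05/3. This is partly by construction: duration is the only confounder simulated, acts linearly and is measured without error.

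**The case against.** The design already limits the problem. Both HIV-infected groups have at least four years of cART and three and a half of suppression, attend one clinic, and are matched on age and comorbidity. The comparison is exploratory, section 10.4 lets its statistics diverge from plan, and section 10.3 allows amendments until database lock, so an adjusted analysis could be added later. All of this is right, and it keeps the point modest. But the floors bound only the lower end of duration, and permission to diverge is not a plan to adjust.

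Three stronger readings are tempting, and the documents support none of them.

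- *That the protocol makes mucosal recovery a function of years on cART.* Section 1.1 says only that restoration is partial after years of treatment. It gives no rate, and its remark on CD4 counts returning to normal concerns CD4 recovery in responders, not the mucosa.
- *That the controls must have been treated longer.* A control who had to climb above 600 cells/μL needs his recovery time plus 3.5 years, whereas a case can enter just past four years. But a control who started with a high count can also enter just past four years, and long-treated INR men are fully eligible. The direction is open.
- *That the error rate reaches about a third.* A two-group test at 5% would give 7% to 34% in the same four scenarios (the d = 0.5 case is 33.8%). That is not the planned test; the Bonferroni post-test gives the lower figures in the table.

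**Conclusion.** The point stands as a gap in the control of confounding in a secondary, exploratory comparison. It is not evidence that the comparison is biased. Whether bias arises depends on two quantities that the documents do not give: the difference in cART duration between the groups, and how strongly duration tracks each marker. With no duration gap there is no inflation. Over the assumed range, the planned post-test makes a false INR finding in about 3% to 20% of trials against a nominal 1.7%, and an opposing gap of the same size cuts power for a large true difference from 81% to between 66% and 25%. The contrast with HIV-negative men is outside this point, since they take no cART, and the primary safety objective is untouched. The change is worth making because it is cheap and can be specified before the data are seen.

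**What to change.** 1. **Section 10.3.1:** tabulate years on cART at week 0 (median, quartiles, range) for the INR and non-INR groups.
2. **Section 10.4, single variables:** keep the three-group test. Add, for INR versus non-INR only, a regression of the ranked variable on group and years on cART at week 0. Name it as the analysis on which any claim of an INR versus non-INR difference rests, and state its threshold; keeping 0.05/3 preserves the stringency of the post-test.
3. **Section 10.4, microbiota composition:** include years on cART as a covariate in the permutation test for the same contrast. Otherwise hypothesis i stays unadjusted.
4. **Section 3 (optional):** match HIV-infected controls on cART duration where the pool allows. Section 10.1 says that the number of eligible patients already influenced the sample size, so this should not be a condition.

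**Cost.** No new data should be needed: section 6.2 collects "Medical history (including disease history and corresponding treatment details", and checking the four-year criterion already needs treatment history. The model spends one degree of freedom among 40 men. The standard error of the group effect is multiplied by √(1 + Δ²/4), which is 1.03 for a 0.5 SD gap and 1.12 for a 1 SD gap. Part or all of that is recovered through the variation that duration explains, a factor √(1 − r²) of 0.95 to 0.87. Adjustment does not protect against other differences between the groups.
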